6.4.1.4 Non-enzyme inducing anti-epileptic drugs

Non-enzyme inducing anti-epileptic medication (Non-EIAED) is allowed.

6.4.1.5 Palliative radiotherapy and surgery

Local radiotherapy for isolated brain progression, for analgesic purposes or for lytic lesions at risk of fracture may be carried out if required. If palliative radiotherapy is initiated after start of study treatment, the reason for its use must be clearly documented and progression as per RECIST 1.1 must be assessed and documented.

Patients who develop progressive disease but are still deriving clinical benefit from LDK378 therapy, as determined by the Investigator may undergo radiotherapy and/or surgical resection as palliative localized therapy to treat metastatic lesions. LDK378 should be held for at least 4 days prior to radiotherapy and at least 1 day prior to any surgery. LDK378 may be resumed ≥ 3 days after completing radiotherapy or minor surgery, and ≥ 2 weeks after major surgery.

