6.1.3 Treatment duration

Patients will continue LDK378 until they experience any of the following:

- Disease progression (radiologically documented according to RECIST 1.1 by the investigator). LDK378 therapy will continue until progressive disease if clinically acceptable. However, LDK378 may be continued beyond RECIST-defined progressive disease (PD) as assessed by the investigator, if in the judgment of the investigator, there may be clinical benefit with continued treatment.
- Unacceptable toxicity that precludes further treatment
- Start of a new anti-cancer therapy
- Pregnancy
- Treatment is discontinued at the discretion of the investigator or patient
- Lost to follow-up
- Death
- Study terminated by Sponsor

Patients who permanently discontinue the study drug for any reason other than disease progression must, if agreeing to further follow-up, continue efficacy assessments as scheduled in the protocol until the time of confirmed disease progression.

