6.4.2 Prohibited concomitant therapy

6.4.2.1 Other anticancer therapy

Anticancer therapy (chemotherapy, targeted therapy, biologic therapy or radiation therapy [except palliative radiotherapy as described in [Section 6.4.1.5](#)], anti-cancer surgery and

immunotherapy) other than the study treatment must not be given to patients while they are enrolled in the treatment portion of the trial. If such agents are required then the patient must be permanently discontinued from the treatment portion of the study.

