Only tumor assessments performed before the start of any further antineoplastic therapies (i.e., any additional secondary antineoplastic therapy or anticancer surgery) will be considered in the assessment of BOR. If a patient receives any further antineoplastic therapy while on study, any subsequent tumor assessments will be excluded from the BOR determination. Further antineoplastic therapies will be identified via protocol deviations (deviation code: COMDxx for use of prohibited concomitant therapy including other anticancer therapy, where xx is a serial number, e.g. COMD01, COMD02) or from the data collected on the [Antineoplastic Therapy Since Discontinuation of Study Treatment] eCRF pages, as appropriate. Clinical deterioration will not be considered as documented disease progression.

For patients with BOR of UNK, the reason for having unknown status will be listed. The following reasons will be used:

- No valid post-baseline assessment
- All post-baseline assessments have overall response UNK
- New antineoplastic therapy started before first post-baseline assessment
- SD too early (≤6 weeks after start date of study drug)
- PD too late (>12 weeks after start date of study drug)

Special (and rare) cases where BOR is 'Unknown' due to both early SD and late PD will be classified as 'SD too early'.

Frequency counts and percentages of patients with each BOR will be reported along with ORR and DCR.

Disease control rate

Disease control rate (DCR) is defined as the proportion of patients with a best overall response of CR, PR or SD, as assessed per RECIST 1.1 by the investigator.

DCR will be estimated and the exact 95% CI will be provided.

Time to response

Time to response (TTR) is defined as the time from the start date of study drug to the date of first documented response (PR or CR, which must be confirmed subsequently) for patients with a confirmed response (PR or CR) as assessed per RECIST 1.1 by the investigator.

TTR will be summarized using descriptive statistics for patients with a confirmed response (PR or CR). In addition, TTR will be summarized in 2-month intervals.

Duration of response

Duration of response (DOR) is defined as the time from the date of first documented response (PR or CR) to the date of first documented disease progression (PD) or death due to any cause among patients with a confirmed response (PR or CR) as assessed per RECIST 1.1 by the investigator.

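### Protocol 6.4.1.5 lets LDK378 resume after palliative resection of a metastasis, but 6.4.2.1 bars anti-cancer surgery on treatment and requires permanent discontinuation; the two sections must be reconciled

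*Protocol*

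**What the plan says.** Protocol 6.4.1.5, in the part on permitted therapy, covers patients who have progressed but in the investigator's view still benefit from LDK378. Such patients "may undergo radiotherapy and/or surgical resection as palliative localized therapy to treat metastatic lesions". The drug is paused rather than stopped: "LDK378 should be held for at least 4 days prior to radiotherapy and at least 1 day prior to any surgery". It can then be restarted: "LDK378 may be resumed ≥ 3 days after completing radiotherapy or minor surgery, and ≥ 2 weeks after major surgery".

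Protocol 6.4.2.1, in the part on prohibited therapy, lists anticancer treatments that may not be given during the treatment portion. After radiation therapy the list reads "except palliative radiotherapy as described in [Section 6.4.1.5](#)], anti-cancer surgery and" immunotherapy. The consequence is stated without exception: "If such agents are required then the patient must be permanently discontinued from the treatment portion of the study".

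Three other places bear on the point:

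- Protocol 6.4 allows concomitant therapy under 6.4.1 unless 6.4.2 specifically prohibits it.
- Protocol 6.1.3 ends treatment on "Start of a new anti-cancer therapy", with no carve-out for palliative procedures.
- SAP 2.6 reports patients who receive prohibited concomitant therapy as protocol deviations.

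**The concern.** The same operation is a reason to pause LDK378 in one section and to stop it for good in the other. The exemption in 6.4.2.1 points to 6.4.1.5 by number but picks up only radiotherapy, although that section deals with radiotherapy and surgery together.

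Treatment beyond PD is a stated feature of the trial (Protocol 4.1 and 6.1.3), so the situation is foreseen. Two sites with the same patient could act differently, each relying on a current section. One patient would go on with dosing and scans, and the other would move to end of treatment. The patient who continues, handled as 6.4.1.5 allows, could also be reported as a deviator.

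**Working it through.** No figure in the plan is at issue, so the check is a comparison of texts, with one small calculation on the safety window.

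**Step 1. Do both sections govern the same act?** A patient under 6.4.1.5 is still on LDK378 and so is in the treatment portion. The 6.4.2.1 ban covers that whole portion and makes no exception after PD. The resection in 6.4.1.5 is directed at metastases. Nothing in either document defines anti-cancer surgery so as to leave that out.

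**Step 2. Is the surgery exempted?** No. The bracket in 6.4.2.1 names palliative radiotherapy only. Since palliative radiotherapy needed naming, palliative intent alone does not take a treatment off the list.

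**Step 3. Which section takes precedence?** Under 6.4 the permission gives way to the prohibition. Read literally, the restart times after surgery then have nothing to apply to.

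**Step 4. Does other text settle it?** No. Protocol 6.1.3 does not mention surgery. The mandatory-stop list in 7.1.3 refers to Appendix 1, which contains only drug lists. Protocol Section 12 bars investigators from asking the sponsor to approve a deviation.

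**Step 5. What differs between the two readings?**

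| Item | 6.4.1.5 followed, drug restarted | 6.4.2.1 followed |
|---|---|---|
| Dosing | Paused, then resumed | Permanently stopped |
| Post-PD scans (Protocol 4.1) | Continue until LDK378 is permanently stopped | End |
| Exposure (SAP 2.6) | Runs to the later last dose, with the pause counted in its duration | Ends at the last dose before surgery |
| Disposition (SAP 2.5) | Still on treatment, or discontinued later | Discontinued at surgery |
| On-treatment window (Protocol 10.5.3.1, SAP 2.8.2) | To 30 days after the later last dose | To 30 days after the pre-operative last dose |
| Deviation (SAP 2.6) | Reportable if 6.4.2.1 is applied literally | None if treatment was stopped as required |

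**Step 6. How much post-operative safety data depends on the reading?** If the last dose is *h* days before surgery and the drug is not restarted, the window covers 30 − *h* days after surgery.

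- *h* = 1 gives 30 − 1 = 29 days.
- *h* = 2 gives 30 − 2 = 28 days.
- *h* = 7 (a longer pause, assumed for illustration) gives 30 − 7 = 23 days.

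With a pause near the 1-day minimum, about four weeks of post-operative events are on-treatment under either reading. Only the period after that differs.

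**Step 7. Are efficacy endpoints touched?** Under Protocol 10.4.3 and SAP 2.7.3, assessments after first documented progression are not used for ORR, and the same applies to the secondary efficacy endpoints. Surgery under 6.4.1.5 follows PD, so ORR, best overall response, DOR and PFS are already fixed.

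**The case against.** The best defence is that 6.4.1.5 is the specific rule. It is limited to PD with continuing benefit and separates minor from major surgery. The Amendment 1 log says it was revised to clarify interruption and re-initiation around radiotherapy and surgery, so the provision looks deliberate. The ban, by contrast, uses a general term and then speaks of agents, which could mean drugs. This does suggest what the authors may have intended. It does not resolve the text: 6.4 sets the opposite order of precedence, the agents in question are those of a list that includes radiation and surgery, and the explicit radiotherapy exemption tells against an unstated one for surgery.

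Other objections limit the point, and they stand. A reader might infer any of the following, and the documents do not support them:

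- **A site cannot comply with both sections.** Section 6.4.1.5 is permissive. A site that permanently stops LDK378 and then operates breaks neither section. The defect is a permission given in one place and withdrawn in another.
- **Post-operative adverse events are lost.** The 30-day window captures most of them, and SAP 2.8.2 still lists and flags later safety data.
- **Exposure data are removed.** A patient who stops has no later exposure to record. The summaries would correctly show what was given.
- **Response is affected through SAP 2.8.1.** That section treats "any additional secondary antineoplastic therapy or anticancer surgery" as further therapy and uses deviation codes as one way of finding it. After first PD this changes no best overall response.
- **Deviation counts will certainly differ by site.** The deviation definitions are in a separate specification and are finalised before database lock (SAP 2.4). Whether they capture palliative resection cannot be seen from these documents.

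**Conclusion.** The contradiction is real and is in the current text. Palliative resection after PD is both permitted with restart of LDK378 and, by a provision that takes precedence under 6.4, prohibited with permanent discontinuation. It should be corrected because it governs conduct, but it does not threaten the primary estimate.

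The reach is narrow: continuation of treatment and post-PD scans after such surgery, the exposure, disposition and on-treatment window that follow, and possible reporting as a prohibited-therapy deviation. The documents give no frequency for these operations. With about 20 patients, each one affected is 1/20 = 5% of the Safety Set, which is a unit and not an expected effect. The visible SAP plans no separate analysis of treatment beyond PD.

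The conclusion rests on two assumptions. First, anti-cancer surgery includes palliative resection of metastases, since nothing distinguishes them. Second, the PD that opens 6.4.1.5 is documented under RECIST 1.1. The statement that efficacy endpoints are already fixed depends on this, because SAP 2.8.1 does not count clinical deterioration as progression.

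**What to change.** Reconcile 6.4.1.5 and 6.4.2.1 so that palliative surgery has one status. The wording could either bring the surgery of 6.4.1.5 into the exemption in 6.4.2.1 or remove the surgical provision from 6.4.1.5. The choice is clinical and belongs to the sponsor. Then make the new-therapy stopping criterion in 6.1.3 and the prohibited-therapy entry in the deviation specification match that choice, so that a patient managed as the protocol allows is not reported as a deviator.

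The cost is about one sentence in the next amendment, a matching adjustment to 6.1.3 if needed, and one line in the deviation specification before database lock. No patients, procedures or analyses are added.

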6.4.1.6 Gastric protection agents

The use of gastric protection agents including antacids, H2-antagonists, and proton pump inhibitors (PPIs) is allowed [Table 14-2](#) of Appendix 1). However, PPIs should be used with caution due to the theoretical effects of long-acting pH elevating agents (i.e., prolonged acid suppression) on reducing LDK378 absorption. When the concurrent use of a H2-antagonist or an antacid with LDK378 is necessary, the H2 blocker must be administered 10 hours before or 2 hours after the LDK378 dose, and the antacid must be administered 2 hours before or 2 hours after the LDK378 dose. Time restrictions for the concurrent use of PPIs and LDK378 are not applicable due to the long-acting effects of PPIs on gastric pH (i.e., separation of doses will not likely impact this interaction).

6.4.2 Prohibited concomitant therapy

6.4.2.1 Other anticancer therapy

Anticancer therapy (chemotherapy, targeted therapy, biologic therapy or radiation therapy [except palliative radiotherapy as described in [Section 6.4.1.5](#)], anti-cancer surgery and

immunotherapy) other than the study treatment must not be given to patients while they are enrolled in the treatment portion of the trial. If such agents are required then the patient must be permanently discontinued from the treatment portion of the study.

6.4.2.2 Other investigational therapies

Other investigational therapies must not be used while the patient is on the study.

6.4.2.3 Warfarin and coumarin derivatives

Warfarin sodium or any other coumarin-derivative anticoagulant are not permitted. LDK378 is an inhibitor of CYP2C9, the major metabolizing enzyme of warfarin. A clinically relevant increase in warfarin exposure is possible.

6.4.2.4 Enzyme inducing anti-epileptic drug

Use of EIAEDs is not permitted. Refer to [Table 14-3](#) of Appendix 1 for a list of prohibited EIAED.

If a patient is currently taking an EIAED, he/she must have discontinued the EIAED therapy for at least 1 week prior to starting study drug.

If a patient was previously on a non-EIAED and needs to permanently change anticonvulsant agent but cannot change to another non-EIAED, the patient will be taken off LDK378.

6.4.2.5 Strong CYP3A inhibitors and inducers

In vitro metabolism studies suggest that oxidative metabolism of LDK378 is predominantly mediated by CYP3A4/5.

Strong inhibitors or inducers of CYP3A4/5 are prohibited. Patients receiving concomitant medications known to strongly inhibit and/or induce CYP3A4/5 that are deemed medically necessary should be excluded from the study. Refer to [Table 14-1](#) of Appendix 1 for a list of these medications. Please note that this list may not be comprehensive.

6.4.2.6 Medications that are CYP2C9 and CYP3A4/5 substrates with narrow therapeutic index

LDK378 is a potent inhibitor of drugs metabolized by CYP2C9 and CYP3A4/5 *in vitro*. Because of the potential risk for drug-drug interactions, using concomitant medications known to be metabolized by these enzymes and that have a narrow therapeutic index is not permitted concomitantly with LDK378. Refer to [Table 14-1](#) of Appendix 1 for a list of these medications. Please note that this list may not be comprehensive.

6.4.2.7 Herbal medications

Herbal preparations/medications are not allowed throughout the study, as a potential drug-drug interaction is always possible. These herbal medications include, but are not limited to: St. John's wort, Kava, ephedra (ma huang), gingko biloba, dehydroepiandrosterone (DHEA), yohimbe, saw palmetto, and ginseng.

Patients should stop using herbal medications at least 7 days prior to first dose of study treatment.

6.4.2.8 Medications that may prolong the QT interval or have a known risk of inducing Torsades de Pointes

LDK378 has potent activity on the hERG channel with an IC_{50} of 0.4 μ M. However there were no LDK378-related effects *in vivo* in monkeys at doses as high as 100 mg/kg (human equivalent dose [HED] of 1950 mg).

Serial ECGs were collected following a single dose and at steady-state to evaluate the effect of LDK378 on the QT interval in an open-label, dose-escalation, and expansion study ([CLDK378X2101]). A total of 304 patients were treated with LDK 378 doses ranging from 50 to 750 mg with 255 patients treated with LDK378 750 mg. One of 304 patients (<1%) was found to have a QTc >500 msec and 10 patients (3.3%) had an increase from baseline QTc >60 msec. A central tendency analysis of the QTc data at average steady-state concentrations demonstrated that the upper bound of the 2-sided 90% CI for QTc was 16 msec at LDK378 750 mg. A pharmacokinetic/pharmacodynamic analysis suggested concentration-dependent QTc interval prolongation.

Concomitant administration of LDK378 with drugs known to have a high risk of increasing the QTc interval, and drugs known to increase the QTc interval that are also primarily metabolized by CYP3A4/5 should be avoided. Concomitant use of LDK378 and any medication included in [Table 14-4](#) of Appendix 1 titled “List of prohibited QT prolonging drugs” (i.e., drugs that are generally accepted by the Qtdrugs.org Advisory Board of the Arizona CERT to have a known risk of causing Torsades de Pointes) is not permitted.

6.5 Patient numbering, treatment assignment or randomization

6.5.1 Patient numbering

[figure not shown]
Each patient is identified in the study by a Subject Number (Subject No.), that is assigned when the patient is first enrolled for screening and is retained as the primary identifier for the patient throughout his/her entire participation in the trial. The Subject No. consists of the Center Number (Center No.) (as assigned by Novartis to the investigative site) with a sequential patient number suffixed to it, so that each patient is numbered uniquely across the entire database. Upon signing the informed consent form, the patient is assigned to the next sequential Patient No. Once assigned, the Patient No. must not be reused for any other patient and the Subject No.

6.5.2 Treatment assignment

Not applicable since this study consists of a single arm and no randomization.

6.5.3 Treatment blinding

Not applicable

6.6 Study drug preparation and dispensation

The investigator or responsible site personnel must instruct the patient or caregiver to take the study drugs as per protocol. Study drug(s) will be dispensed to the patient by authorized site personnel only. All dosages prescribed to the patient and all dose changes during the study must be recorded on the Dosage Administration Record eCRF.

The site pharmacy will receive open label medication containing LDK378 capsules. Medication will be dispensed based on the appropriate dose with instructions from the investigator on how to take the medication.

6.6.1 Study drug packaging and labeling

Medication labels will be in the local language and comply with the legal requirements of country. They will include storage conditions for the drug but no information about the patient.

6.6.2 Drug supply and storage

Study treatments must be received by designated personnel at the study site, handled and stored safely and properly, and kept in a secured location to which only the investigator and designated site personnel have access. Upon receipt, the study treatment should be stored according to the instructions specified on the drug labels and in the [Investigator's Brochure].

6.6.3 Study drug compliance and accountability

6.6.3.1 Study drug compliance

Compliance will be assessed by the investigator and/or study personnel at each patient visit and information provided by the patient and/or caregiver will be captured in the Drug Accountability Form. This information must be captured in the source document at each patient visit.

Compliance will be assured by administrations of the study treatment under the supervision of investigator or his/her designee.

Site personnel will add the patient number on the label. Immediately before dispensing the package to the patient, site personnel will detach the outer part of the label from the packaging and affix it to the source document (Drug Label Form) for that patient's unique patient number.

6.6.3.2 Study drug accountability

The investigator or designee must maintain an accurate record of the shipment and dispensing of LDK378 study treatment in a drug accountability log. Drug accountability will be noted by the field monitor during site visits and at the completion of the study. Patients will be asked to return all unused LDK378 study treatment and packaging on a regular basis, at the end of the study or at the time of study treatment discontinuation.

At study close-out, and, as appropriate during the course of the study, the investigator will return all used and unused study treatment, packaging, drug labels, and a copy of the

completed drug accountability log to the Novartis monitor or to the Novartis address provided in the investigator folder at each site.

6.6.3.3 Handling of other study treatment

Not applicable

6.6.4 Disposal and destruction

The study drug supply can be destroyed at the local Novartis facility, Drug Supply group or third party, as appropriate.

7 Visit schedule and assessments

7.1 Study flow and visit schedule

Table 7-1 lists all of the assessments and indicates with an “X” the visits when they are performed. Each treatment cycle is 28 days (the 28 days cycle length is fixed regardless of whether the dose of LDK378 is withheld). All visits are to be scheduled according to the appropriate number of calendar days from Cycle 1 Day 1 of study drug administration. A visit window of +/- 1 day in Cycle 1 and +/- 3 days in Cycle 2 onwards is allowed. Imaging evaluations may be performed +/-7 days of the due date of the assessment.

Note: If treatment with LDK378 is withheld at any time during the study, all study visits, safety and efficacy assessments should continue according to the appropriate number of calendar days from Cycle 1 Day 1 as per the schedule of assessments.

All data obtained from these assessments must be supported in the patients’ source documentation. No eCRF will be used as a source document. The table indicates which assessments produce data to be entered into the database (D) or remain in the source documents only (S).

Visit name	Category	Protocol Section	Screening Phase	Treatment Phase				Post treatment follow up phase			Survival follow-up phase
				Cycle 1 (28 d)		Subsequent cycles (28 d)	End of study Treatment (EOT)	30-day safety follow-up	Tumor follow- up if no PD at the EOT	Study phase completion	
Screening Visit (Day -28 to Day -1)				Cycle 1 Day 1	Cycle 1 Day 15	Day 1	End of treatment visit				
Antineoplastic therapies since discontinuation of study treatment	D	7.1.5.3.						X	X		X Every 12 weeks
Survival assessment	D	7.1.5.3.									X Every 12 weeks

